APPENDIX J. SUBSTUDY TO PROTOCOL ALK3831-A304 (PARTICIPATING SITES ONLY)

Introduction and Rationale for the Substudy

In addition to standard efficacy and safety endpoints collected in a clinical trial of a new therapeutic treatment, patient and caregiver perspectives are useful in further describing the overall patient experience. Patients' and caregivers' experiences with the disease or with specific therapies can provide information on important disease concepts, including impacts on quality of life and preferences with regard to treatment options. Such data are valuable to inform clinical development of new therapies.

Patient and caregiver experience data may be collected using quantitative, qualitative, or mixed methodology. An important advantage of qualitative methodology is its ability to discover information not covered in standard structured questionnaires or rating scales.

To obtain patient experience data from subjects treated with ALKS 3831, this substudy will use in-depth, qualitative interviews to collect subjects' and caregivers' feedback on their experiences in study ALK3831-A304. The interviews will follow semi-structured interview guides to capture spontaneous, as well as probed, descriptions of treatment experience. This exploratory qualitative approach is intended both to assess *a priori* concepts of interest and to explore the disease burden and treatment experiences of patients and caregivers with schizophrenia prior to and during participation in study ALK3831-A304.

Substudy Objectives

The main objectives of this substudy are to explore the burden of living with schizophrenia and the treatment experiences of subjects who have completed or discontinued prematurely from study ALK3831-A304. Additionally, experiences of subjects' caregivers will be examined. Interviews will focus on concepts relevant to the subject's and caregiver's experience with the burden of disease, impacts of treatment with ALKS 3831 on daily life, and impacts of participation in the ALK3831-A304 Study. The interviews will also probe on specific treatment attributes liked/disliked by subjects, the degree of patient satisfaction/dissatisfaction with the ALKS 3831 treatment and study, and subjects' and caregivers' comparisons of the ALKS 3831 treatment experience with previous treatment experiences.

Selection and Withdrawal of Subjects

Substudy Sites

A subset of sites with subjects enrolled in ALK3831-A304 will be eligible to participate in the substudy. Approval from the appropriate IEC/IRB must be obtained for each site participating in the substudy.

Substudy Participants

Approximately 50 subjects who participated in ALK3831-A304 and approximately 15 of their caregivers are expected to participate in the substudy. Subjects who enroll in the substudy will have completed study procedures for the end of treatment/early discontinuation visit described in [Section 8.2](#) and will meet the criteria for inclusion in the substudy.

Subject Inclusion Criteria

Selection of subjects to be interviewed will be based on the following inclusion criteria:

1. Subject is willing and able to provide written informed consent.
2. Subject has completed or prematurely discontinued from study ALK3831-A304.
3. Subject speaks English fluently.
4. Subject is willing and able to participate in a 60-minute interview.
5. If not participating in study ALK3831-A308, subject agrees to schedule an interview within 60 days of completing or prematurely discontinuing from study ALK3831-A304. If subject is participating in study ALK3831-A308, the interview may be conducted at any time after completing study ALK3831-A304.

There is no exclusion criterion for participants of this substudy; any subject who meets the inclusion criteria may participate.

Caregiver Inclusion Criteria

Caregivers of subjects participating in the ALK3831-A304 substudy will be selected for interview based on the following inclusion criteria:

6. Subject has provided written informed consent to allow caregiver to be interviewed regarding subject's condition and treatment experience.
7. Caregiver must be willing and able to provide written informed consent to participate in the substudy.
8. Caregiver is in contact several times per week with the subject participating in the substudy. Caregivers can be family members, friends, or paid professional caregivers. Caregivers may provide full- or part-time help to the person with schizophrenia.
9. Caregiver speaks English fluently.
10. Caregiver is willing and able to participate in a 60-minute interview, either in person or via telephone.

There is no exclusion criterion for caregivers participating in this substudy; any caregiver who meets the inclusion criteria may participate.

Subject or Caregiver Withdrawal

A subject or caregiver may withdraw consent to participate in this substudy at any time. A subject who chooses to withdraw consent to participate in the substudy may continue full participation in any other ongoing ALKS 3831 study, as eligible.

Substudy Design

This is a qualitative study involving interviews with approximately 50 subjects who have either completed or prematurely terminated participation in ALK3831-A304, and with approximately 15 of their caregivers. Subjects will return to the clinical site for an interview within 60 days of completing Visit 27, or at any time if continuing in study ALK3831-A308. Interviewers will follow standardized, semi-structured Interview Guides developed specifically for the study. Caregivers will be interviewed by phone/webcam to explore their perspectives of subjects' treatment and study experience. Qualitative analysis will involve scoring transcribed interviews for concepts that emerge during the substudy.

Substudy Procedures

Informed consent for participation in substudy

Each subject and caregiver must provide written informed consent to participate in the substudy prior to scheduling an interview. In addition, for each participating caregiver, written informed consent for the caregiver to be interviewed regarding the subject's condition and treatment experience must be obtained from the subject.

Concept Elicitation Interviews

Interviewers

All interviews will be conducted by qualitative researchers with experience and training in conducting qualitative interviews.

Patient Concept Elicitation Interviews

The goal of the Patient Concept Elicitation interview is to gain insight into how living with and being treated for schizophrenia impacts the way the subjects feel and function in daily life, and to document preferences and comparative information about current and prior treatment experiences.

Interviewers will follow the Subject Interview Guide containing questions designed to document concepts related to schizophrenia including, but not limited to burden of disease, physical function, role function, social function, and overall treatment experiences, as well as satisfaction and preferences regarding treatment received during and prior to participation in study ALK3831-A304.

Questions in the interview guide will utilize a standardized methodology for collecting subjects' responses to open-ended questions, and following up by probing to elicit more specific and nuanced detail.

Interviews will be conducted with the subject present at the clinical site. The interviewer may participate either in person or by videoconference. At the start of the interview, the interviewer will confirm that each participant understands and has signed the ICF.

Each interview will last approximately 60 minutes and will include an introduction (approximately 5 minutes), a concept elicitation portion (approximately 50 minutes), and a conclusion (approximately 5 minutes). After several interviews have been completed and transcripts have been reviewed, the Subject Interview Guide may be revised to capture emergent concepts and to pose questions more effectively.

Caregiver Concept Elicitation Interviews

Each subject will be asked during the in-person concept elicitation interview whether the subject's caregiver might be agreeable to participating in a separate telephone interview. If so, the subject will be asked for written consent for the subject's caregiver to be interviewed, and will be provided with contact information to share with the caregiver for the purpose of scheduling a telephone interview.

Caregivers of subjects participating in this substudy will be interviewed by telephone or videoconference/telephone. The design of the concept elicitation interview with caregivers will mirror that for concept elicitation interviews of subjects; however, questions in the Caregiver Interview Guide will be designed to elicit a caregiver's feedback on a subject's experiences with schizophrenia, particularly the burden of disease, as well as treatment preferences and treatment satisfaction. Additionally, caregivers will be asked to share experiences around the burden of caring for someone with schizophrenia, impact of this burden on quality of life, and impressions of treatment successes and challenges, as well as experiences in caring for a clinical trial participant. Although all caregiver interviews will be conducted remotely, other aspects of interview procedures will be similar to those for subject interviews.

Statistics

Data Coding

Interview transcripts will be independently coded using content thematic analysis, in accordance with Grounded Theory methods [(Corbin and Strauss 2008), Chapters 8 through 11; (Patrick et al, 2011)]. Coding will be verified by two trained qualitative researchers until saturation (the point at which no new information emerges) is reached. Coding will occur after each round of interviews, enabling results to inform refinement of subsequent interviews.

Data Analysis

To identify patterns in responses and confirm important concepts reported by subjects with schizophrenia and their caregivers (eg, burden of disease, areas of impact related to patients' quality of life, overall treatment experiences, treatment satisfaction, and treatment preferences), coded transcripts will be reviewed for emerging themes [(Corbin and Strauss 2008), Chapter 8]. This methodology allows identification of new concepts emerging from interviews with patients or caregivers, rather than limiting inquiry to concepts imposed by a predetermined theory. All qualitative data obtained from substudy interviews will be analyzed using NVivo qualitative research software, version 11.0 (NVivo qualitative data analysis software; QSR International PTY Ltd. Version 11, 2015). Final details of the analysis will be captured in a substudy data analysis plan. Results from this substudy will be provided in an addendum to the clinical study report for ALK3831-A304.

Safety Reporting

The interview guide will not include any question regarding a specific adverse event (AE). Interviewers will be trained to inform the Principal Investigator of any unsolicited AE reported during the interview upon conclusion of the interview. Adverse events and serious AEs (SAEs) will be reported in accordance with [Section 13 of the protocol](#).

Ethical Considerations

Institutional Review Board

The responsible IRB ([Section 17.1 of the protocol](#)) for each site participating in the substudy must review and approve protocol sections describing the substudy, the Subject Interview Guide, and any revisions made, as well as information on the substudy to be provided to participating subjects and caregivers in obtaining written informed consent.

Ethical Conduct of the Substudy

This substudy will be conducted in accordance with the protocol, the ICH Guideline E6, and all applicable local regulatory requirements. Alkermes is committed to complying with this standard to provide assurance that the rights, safety, and well-being of study subjects will be protected, consistent with the principles having their origin in the Declaration of Helsinki.

Written Informed consent

In addition to written informed consent previously obtained from subjects to participate in the main study ALK3831-A304, all subjects and caregivers who voluntarily agree to participate in this substudy must provide separate written consent to the interview, to interview recording, and to subsequent analysis of interview responses.

Data Handling and Recordkeeping

Data Capture

Subjects will be interviewed at the clinical trial site by interviewers participating either in person or through videoconference. Caregivers will be interviewed via telephone or videoconference/telephone.

In-person interviews will be audiotaped using digital audio-recorder equipment and later transcribed verbatim. Telephone interviews will be recorded using WebEx and a back-up audio recorder. Recordings will be sent to a qualitative research vendor via a secure file transfer system to be transcribed verbatim. The qualitative vendor will redact all personal information from the transcript before submitting back via the secure file transfer system.

Interview transcripts will be independently content-coded and verified by two trained qualitative researchers. Coding will be reviewed by a senior qualitative scientist. Any identified discrepancy between coders will be reviewed, discussed, and resolved by the substudy research team.

Retention of Records

All participant records will be archived consistent with International Council for Harmonisation Good Clinical Practice (ICH-GCP) and Health Insurance Portability and Accountability Act (HIPAA) regulations. All paper copies of documents, audio recordings, and electronic files will be saved in a secure system following HIPAA regulations. Any written or printed study documents will be collected and filed in a locked filing cabinet. Records, including the electronic versions of the responses and scores, will be maintained indefinitely or until the sponsor requests destruction.

Subject Confidentiality

All transcripts will be labeled only with the unique participant subject or caregiver identification number; no identifying information will be included in the transcript. Alkermes will not receive any identifying information from the study participants. Auditors and other authorized agents of Alkermes will be granted direct access to the study participant data, without violating the confidentiality of the participant, to the extent permitted by law and applicable regulations. Participants' identities will remain confidential in any presentation of the results of this substudy at meetings or in publications.

HbA1c	Hemoglobin A1c
IWQOL	Impact of Weight on Quality of Life
MedDRA	Medical Dictionary for Regulatory Activities
OLZ	Olanzapine
PANSS	Positive and Negative Syndrome Scale
PCS	Potentially clinically significant
PK	Pharmacokinetics
PT	Preferred term
KM	Kaplan-Meier
QTcF	QT corrected with Fridericia formula
SAE	Serious adverse event
SAP	Statistical analysis plan
SAS	Simpson-Angus Scale
SD	Standard deviation
SMQ	Standardized MedDRA queries
SOC	System organ class
TEAE	Treatment-emergent adverse event

Abbreviation or Term	Explanation or Definition
ULN	Upper limit of normal
VAS	Visual analogue scale
WHO	World Health Organization

1. INTRODUCTION

This statistical analysis plan (SAP) describes the statistical methods to be used for analyses and presentation of safety and efficacy data for the study ALK3831-A304. ALK3831-A304 is a 52-week, open-label safety extension study of ALK3831-A303. This document has been prepared based on Alkermes [ALK3831-A304](#) Study Protocol Amendment 3.0 (dated 26 April 2018)¹.

1.1. Study Objectives

1.1.1. Primary Objective

The primary objective of this study is to evaluate the long-term safety and tolerability of ALKS 3831 in subjects with schizophrenia.

1.2. Summary of the Study Design

Subjects are eligible to be enrolled in the study within 7 days after completing the 24-week treatment period of the antecedent study, ALK3831-A303.

Subjects enrolled in the study will be started on the same olanzapine dose that they had maintained at the end of ALK3831-A303. Subjects taking 20 mg olanzapine (either as OLZ 20 or ALKS 3831 20/10 [20 mg olanzapine/10 mg samidorphan]) will start on ALKS 3831 20/10 in this study and subjects taking 10 mg olanzapine (either as OLZ 10 or ALKS 3831 10/10 [10 mg olanzapine/10 mg samidorphan]) will start on ALKS 3831 10/10 in this study. An intermediate dose, ALKS 3831 15/10 (15 mg olanzapine/10 mg samidorphan), will also be available, and subjects may be titrated to this dose any time after the start of the study at the investigator's discretion. Dosing is flexible throughout the study; however, frequent adjustments are discouraged. Dose adjustments can only be performed on-site at the study center. Subjects requiring dose adjustments between scheduled visits should arrange an unscheduled visit for the following procedures: study drug return, adherence review, adverse event monitoring, and study drug dispensation. Safety assessments will include AE monitoring, clinical laboratory testing, vital signs, weight and waist circumference assessments, 12-lead ECGs, movement disorder assessments, including the Abnormal Involuntary Movement Scale (AIMS), Barnes Akathisia Rating Scale (BARS), Simpson Angus Scale (SAS), and the Columbia-Suicide Severity Rating Scale (C-SSRS).

[figure not shown]
Efficacy assessments to evaluate the durability of treatment effect will include Positive and Negative Syndrome Scale (PANSS) and Clinical Global Impressions-Severity (CGI-S).

Additional assessments include Impact of Weight on Quality of Life–Lite Questionnaire (IWQOL-Lite), Cigarette Use, and EuroQOL-5D (EQ-5D).

Subjects completing 52 weeks of treatment with study drug will be eligible to continue in another open-label, long-term safety study ([ALK3831-A308](#)) and will continue to receive ALKS 3831. Subjects not continuing in the ALK3831-A308 long-term safety study will enter a 4-week Safety Follow-up Period.

A schematic of the study design is provided in [Figure 1](#).

Figure 1: Study Design Schematic

*Visits will occur biweekly throughout the 52-week Treatment Period. Subjects will start the study on the equivalent olanzapine dose to what they maintained at the end of ALK3831-A303. The dose may be adjusted to either 10/10, 15/10, or 20/10 mg throughout the study period, based on Investigator discretion, and such dose adjustments will require subjects to visit the study site.

2. SAMPLE SIZE CONSIDERATION

No formal sample size calculation is performed for this extension study. A sample size of approximately 540 is based on the estimated maximum number of subjects who might be expected to continue from the ALK3831-A303 study.

3. DATA ANALYSIS

3.1. General Statistical Methodology

Baseline for efficacy or safety analysis is defined as the last non-missing assessment before the first dose of ALKS 3831 in the ALK3831-A304 study, and it will be used for all efficacy and safety analysis, unless specified otherwise.

Baseline of precedent study (A303) is defined as the last non-missing assessment before the first dose of study drug in the ALK3831-A303 study. It will be used for the summary of the PANSS total score and subscales and body weight results.

Treatment sequence is defined according to the treatment assignment in antecedent and current studies as ALKS 3831/ALKS 3831 (ALKS 3831 in both ALK3831-A303 study and ALK3831-A304 study) and OLZ/ALKS 3831 (olanzapine in ALK3831-A303 study and ALKS 3831 in

ALK3831-A304 study). All efficacy and safety analysis will be presented by treatment sequence and overall.

In general, descriptive statistics: n, mean, standard deviation (SD), median, minimum, and maximum, for continuous variables and number and percentage of subjects in each category for categorical variables will be provided.

All source data will be presented as subject data listings.

3.2. Definitions of Analysis Populations

3.2.1. Safety Population

The Safety Population will include all subjects who enrolled and received at least one dose of ALKS 3831 in the ALK3831-A304 study. All analyses will be conducted using the Safety Population except for AEs in the safety follow-up period and AE to evaluate the potential for drug withdrawal and dependence. The populations used for the analyses of these events are specified below.

3.2.2. Follow-up Safety Population

Follow-up Safety Population will be defined with respect to the 5 half-lives of the product as subjects in the Safety Population and met any of the following criteria:

- Completed at least one follow-up visit after >7 days of the last dose of ALKS 3831
- Reported at least one AE reported after >7 days of the last dose of ALKS 3831

This population will be used to analyze the AEs in the safety follow-up period.

3.2.3. Post-discontinuation Safety Population

Post-discontinuation Safety Population will be defined as subjects in the Safety Population and met any of the following criteria:

- Completed at least one follow-up visit after >2 day within 16 days of the last dose of ALKS 3831
- Reported at least one AE reported after >2 day after the last dose of ALKS 3831

AE to evaluate potential for drug withdrawal and dependence emerging following discontinuation of ALKS 3831 will be assessed for this population, during the period of >2 days to 16 days after the last dose of drug for subjects with at least 4 weeks study drug exposure.

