7.3. Subject Withdrawal

A subject may be discontinued from the study at any time if the subject, investigator, or the sponsor determines that it is not in the best interest of the subject to continue participation. If a subject has an absolute neutrophil count (ANC) $< 1.0 \times 10^3$ per μL or glycosylated hemoglobin (HbA1c) $\geq 6.5\%$ at any time during this extension study, the subject will be discontinued from the study. Other reasons for discontinuation include the following:

- Adverse Event (AE)
- Lack of Efficacy
- Lost to follow-up
- Withdrawal by subject
- Protocol Deviation (non-compliance with study drug or study procedures)
- Pregnancy
- Study terminated by sponsor
- Other

If a subject withdraws from the study for any reason, he or she will be asked to return to the clinic for an early termination (ET) visit. The ET visit should be scheduled as close as possible to the subject's last dose and will mimic the assessments scheduled to be conducted at the end of treatment (EOT) visit (Visit 27, [Table 3](#)). Following the ET visit, subjects who discontinue study drug but are willing to come in for further assessments will be asked to complete 2 safety follow-up visits 2 and 4 weeks after the ET visit (same assessments as Visits 28 and 29 in [Table 3](#)). They will then be asked to return to the study center for monthly visits according to the schedule outlined in [Table 3](#) for follow-up weight assessments, adverse events, and documentation of any new antipsychotic medications the subject is taking.

Following ET, any ongoing AEs will be followed until resolution, or until deemed stable by the investigator, or until the subject is deemed by the investigator to be lost to follow-up. If, in the opinion of the investigator, it is necessary to monitor a subject beyond the safety follow-up visit, the follow-up period may be extended as necessary. In such instances, the sponsor and the investigator will agree to an acceptable follow-up schedule.

In the event that a subject chooses to withdraw from the study, the investigator should make a reasonable effort to ascertain the reason(s) for withdrawal, while fully respecting the subject's rights. If the subject fails or refuses to return to the study center, an attempt must be made to contact the subject by telephone in order to assess as many safety and efficacy parameters as possible. All data collected over the telephone must be documented and kept in the subject's record.

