8.2. Schedule of Visits and Assessments

The schedule of visits and assessments is shown in [Table 3](#).

A visit window of ± 2 days is allowed throughout the treatment period and during the follow-up period. For a missed visit, the site must contact the subject to reschedule.

Premature discontinuation procedures are provided in [Section 7.3](#). Subjects who discontinue study drug but are willing to come in for further assessments will be asked to complete the ET visit (same assessments as Visit 27, [Table 3](#)) followed by 2 safety follow-up visits 2 and 4 weeks after the ET visit (same assessments as Visits 28 and 29 in [Table 3](#)). They will then be asked to return to the study center for monthly visits according to the schedule outlined in [Table 3](#), to collect the following information: weight assessments, any new antipsychotic medications the subject is taking, and adverse events.

Table 3: Schedule of Visits and Assessments

Visit ^a	Treatment Period																										Follow-Up Period			
	1 ^b	2	3	4	5	6	7	8	9	10	11	12	13	14	15	16	17	18	19	20	21	22	23	24	25	26	27/ ET	28 ^c	29	
Study week	-	2	4	6	8	10	12	14	16	18	20	22	24	26	28	30	32	34	36	38	40	42	44	46	48	50	52	54	56	
Informed Consent	X																													
Eligibility Criteria	X																													
Pregnancy Testing ^d	X						X					X							X											
Urine Drug Screen ^e	X						X					X							X								X			
Weight ^f		X	X	X	X		X		X		X		X		X		X		X		X		X		X		X		X	
Waist Circumference		X	X	X	X		X		X		X		X		X		X		X		X		X		X		X		X	
Vital Signs ^g		X	X	X	X		X		X		X		X		X		X		X		X		X		X		X		X	
Laboratory Samples ^h			X				X					X							X								X			
ECG			X				X					X							X								X			
Physical Exam			X				X					X							X								X			
PANSS ⁱ		X	X		X		X					X							X								X			
CGI-S		X	X		X		X		X		X		X		X		X		X		X		X		X		X		X	
AE ^j		X	X	X	X	X	X	X	X	X	X	X	X	X	X	X	X	X	X	X	X	X	X	X	X	X	X	X	X	X
ConMed Review ^j		X	X	X	X	X	X	X	X	X	X	X	X	X	X	X	X	X	X	X	X	X	X	X	X	X	X	X	X	X
C-SSRS ^k		X	X	X	X	X	X	X	X	X	X	X	X	X	X	X	X	X	X	X	X	X	X	X	X	X	X	X	X	X

Table 3: Schedule of Visits and Assessments (Continued)

Visit ^a	Treatment Period																											Follow-Up Period	
	1 ^b	2	3	4	5	6	7	8	9	10	11	12	13	14	15	16	17	18	19	20	21	22	23	24	25	26	27/ET	28 ^c	29
Study week	-	2	4	6	8	10	12	14	16	18	20	22	24	26	28	30	32	34	36	38	40	42	44	46	48	50	52	54	56
Abnormal Movement Scales ^l			X				X						X						X								X		
IWQOL			X				X						X						X								X		

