3.9.1.3.2. Analysis of Withdrawal and Dependence

Adverse events with an onset date within 2 weeks (>2 to ≤ 16 days) after the last dose of the study drug in those subjects who have received at least 4 weeks of study drug will be included in the evaluation of the potential for withdrawal and dependence. The selection of AEs per subset will be based on the preferred terms from Customized MedDRA queries (CMQs).

The number and percentage of subjects with such AEs will be summarized in the Post-discontinuation Safety Populations by preferred term for subjects with a duration of study drug exposure ≥ 4 weeks.

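### SAP 3.2.3 caps the qualifying follow-up visit at 16 days after the last dose, so a compliant Visit 28 can fall outside and AE-free subjects are selectively left out of the withdrawal denominator

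*SAP*

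**What the plan says.** SAP 3.2.3 takes subjects in the Safety Population who "met any of the following criteria":

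- visit route: "Completed at least one follow-up visit after >2 day within 16 days of the last dose of ALKS 3831"
- AE route: "Reported at least one AE reported after >2 day after the last dose of ALKS 3831", with no upper time limit.

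SAP 3.9.1.3.2 then summarizes, for subjects with at least 4 weeks of exposure, "Adverse events with an onset date within 2 weeks (>2 to ≤ 16 days) after the last dose of the study drug". The onset window is therefore already bounded there, as it is in the closing sentence of 3.2.3.

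The timing of visits comes from the protocol:

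- Section 7.3 asks early terminators for "2 safety follow-up visits 2 and 4 weeks after the ET visit". It also says "The ET visit should be scheduled as close as possible to the" last dose, and names no maximum interval.
- Section 8.2 gives a ±2-day window that "is allowed throughout the treatment period and during the follow-up period".
- Table 3 puts Visit 27 at week 52 and Visit 28 at week 54 for completers. Its footnotes waive Visits 28 and 29 for subjects who enroll in ALK3831-A308.
- Section 13.4 continues AE collection to Visit 29 or 28 days after the final dose.

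The neighbouring Follow-up Safety Population (SAP 3.2.2) requires a visit more than 7 days after the last dose and sets no upper limit.

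**The concern.** The population rule counts days from the last dose. The visit schedule counts from the ET visit or from study week. A cap of 16 days equals the 2-week target plus the 2-day window, so there is no slack once the last dose comes before the ET or end-of-treatment visit. Tablets are taken preferably at bedtime (Protocol 9.1), so a gap of a day is plausible even when the visit is prompt.

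What is at stake is the denominator of the withdrawal and dependence table. Take two subjects first seen for follow-up on Day 18 after the last dose, with no other qualifying contact. Both have been followed for AEs over Days 3 to 16. The one with any AE after Day 2, even one starting on Day 17, is in the population. The AE-free one is out. Membership then depends on the outcome, and the subjects lost are always event-free.

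**Working it through.** Days are counted from the last dose (Day 0).

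**The plan's own bound.** A 2-day gap plus 2 weeks is 2 + 14 = 16, which reproduces the upper limit in SAP 3.2.3 and 3.9.1.3.2.

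**Early terminators.** Let L be the days from last dose to ET visit (not in the documents; assumed, shown as a range) and w the visit window, −2 to +2. Visit 28 falls on day L + 14 + w and misses the cap if that exceeds 16. The shares treat the five allowed days as equally likely, and ET is taken not to be a follow-up visit.

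| L | Allowed Visit 28 days | After Day 16 | Visit exactly on target |
|---|---|---|---|
| 0 | 12–16 | 0/5 (0%) | 14, inside |
| 1 | 13–17 | 1/5 (20%) | 15, inside |
| 2 | 14–18 | 2/5 (40%) | 16, inside |
| 3 | 15–19 | 3/5 (60%) | 17, outside |
| 4 | 16–20 | 4/5 (80%) | 18, outside |
| 5 or more | 17 or later | 5/5 (100%) | 19 or later, outside |

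**Completers.** Visit 27 is on Day 365 + a of the study and Visit 28 on Day 379 + b, with a and b each −2 to +2. The gap from last dose is 14 + b − a + L.

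- Last dose on the Visit 27 day (L = 0): outside if b − a ≥ 3, which is 2 + 1 = 3 of 25 combinations, 12%.
- Last dose the evening before (L = 1): outside if b − a ≥ 2, which is 3 + 2 + 1 = 6 of 25, 24%.

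**Visit 29 cannot rescue anyone.** For early terminators it falls on day L + 28 + w, so Day 26 at the earliest. For completers the earliest is 28 − 2 − 2 = Day 24. Both are past the cap.

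**If ET counts as a follow-up visit.** An ET visit on Days 3 to 16 itself satisfies the visit route. The rows for L = 3 and above then no longer exclude anyone with a lag up to 16 days, and only L = 1 and L = 2 (20% and 40%) remain exposed.

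**Effect on a percentage (illustration only).** Among subjects followed through Day 16, let p be the true share with a selected AE in the window, q the share with any AE after Day 2, and f the share whose first follow-up visit is after Day 16, unrelated to AE status. The dropped share is f(1 − q), and the reported percentage is p / (1 − f(1 − q)). With p = 5%, all inputs assumed:

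| f | q = 20% | q = 10% |
|---|---|---|
| 10% | 5.4% | 5.5% |
| 20% | 6.0% | 6.1% |
| 40% | 7.4% | 7.8% |
| 60% | 9.6% | 10.9% |

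For example, with f = q = 20%: 0.05 / (1 − 0.2 × 0.8) = 0.05 / 0.84 = 6.0%. With no cap on the visit, f = 0 and the result is 5.0%.

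**The case against.** The strongest reply is that the two routes are alternatives. A reader might infer that a visit within 16 days is required, or that withdrawal events go missing. Neither follows: anyone with an AE on Days 3 to 16 enters by the AE route, so every in-window event is kept. The only effect is a smaller denominator, and overstating a safety percentage is the cautious direction. This stands as a limit on the harm. It does not make the percentages correct.

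A reader might also infer that on-schedule visits generally fall outside. They do not. A Visit 28 exactly on target is inside for lags of 0 to 2 days, and 88% or 76% of the completer combinations are inside. Completers who enter ALK3831-A308 need no follow-up visits at all, whatever the cap.

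A further tempting reading is that the rule both shuts out late early terminators and accepts subjects seen only on Day 3. These need opposite readings of the term follow-up visit. Visit 28 cannot fall as early as Day 3; only an ET visit could. If ET counts, most of the late early terminators are admitted. If it does not, the Day 3 case does not arise. Table 3 places ET in the Treatment Period, but the SAP does not settle the matter.

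Finally, a first contact well after Day 16 relies on recall of Days 3 to 16, so wanting a visit near the window is defensible. But the rule applies that standard only to AE-free subjects, and SAP 3.2.2 has no such cap.

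**Conclusion.** The concern holds in a limited form. Under the current text, a protocol-compliant Visit 28 can miss the 16-day cap whenever the last dose precedes the ET or end-of-treatment visit. For completers it can also do so when the dose is taken on the Visit 27 day and the two visit windows move apart. AE-free subjects in that position are excluded, while subjects seen at the same time who have an AE are included. The withdrawal and dependence percentages are therefore biased upward if any such subjects exist.

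The size is unknown. The lag from last dose to ET is not in the documents, visit days were taken as uniform over the window, and the larger exclusion shares apply only if ET is not a follow-up visit. The inflation table is an illustration, not an estimate. The affected output is a descriptive table by preferred term with no test attached. The point is worth correcting because the cap on the visit adds nothing to the bound already placed on AE onset.

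**What to change.** In SAP 3.2.3:

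1. Remove the 16-day limit from the visit route, so that a completed Visit 28 or Visit 29 more than 2 days after the last dose qualifies.
2. Keep the limit of more than 2 and at most 16 days for AE onset only, as 3.9.1.3.2 already has it.
3. State whether an ET visit counts as a follow-up visit. Admitting subjects on an ET visit alone would bring in some with very short cover, so this should be an explicit choice.
4. Report the number of included subjects whose last contact was before Day 16.

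With the first change, none of the five allowed Visit 28 days is excluded at any lag. The cost is one revised line, one clarification and one count, with no new data. The downside is some reliance on recall when the first follow-up contact is late.
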